9.2. Setting / Study Population

VIR-Life is a roll-over study in adult, HBV-mono-infected CHB patients who started CHB treatment with Viread[®] in GEMINIS. Patients in GEMINIS, and therefore now in VIR-Life, are collected nationwide in a real-life setting at approximately 25 of the initial 35 GEMINIS sites. The study sites are either office based physicians with hepatological focus or hospitals with dedicated hepatological outpatient care units.

If the physician decided to treat and document a patient monoinfected with HBV with Viread[®] in GEMINIS and later in VIR-Life, he/she can document the course of the therapy (at months 48, 60 and 72) within the scope of a non-interventional study (NIS).

Eligibility criteria:

Patients completing 3 years in GEMINIS and still receiving a Viread[®]-containing regimen may roll over into this study

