9.4. Data Sources

The conduct of a non-interventional study (NIS) requires, according to definition of a "non-interventional study" in terms of Guideline on good pharmacovigilance practices (GVP) – Module VIII (Rev 1), that the protocol does not stipulate or dictate on the diagnosis, therapeutic decisions and follow-up of the individual patient. The study only observes and collects the use of a drug and the corresponding clinical outcome by the treating physician in the specific indication.

Clinical data is collected from the physician's documentation of the patient's visit in patient medical records that is closest to the documentation time point (month 48, 60 and 72), each +/- 3 months. Primary data sources are electronic medical records, where available or paper records at the participating sites. This data will then be manually transcribed by the investigator into electronic case record form (eCRF).

In this non-interventional follow up study, the following findings are of special interest and information will be collected accordingly:

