9.4.1. Baseline

VIR-life is the extended follow up of GEMINIS. Therefore, VIR-life baseline data is the data that was collected at GEMINS baseline.

9.4.2. During VIR-Life follow up and at end of follow up (month 48, 60 and 72):

- HBV- virology and serology parameters
- Biochemical serum-parameters
 - ALT
- Renal safety parameters
 - Serum creatinine, eCrCl, serum phosphorus
- Liver synthesis parameters
 - Albumin, bilirubin, thrombocytes, prothrombin time (Quick-Value)
- Liver histology, elastography, incident HCC
- Co-morbidities, Co-infections, alcohol consumption
- Adverse events
- Special Situations; pregnancies, medication error, abuse, misuse, overdose, lack of effect, adverse events in infants following breastfeeding, and adverse events associated with product complaints
- Dosing of Viread[®]
- Combination therapy
- Reason for discontinuation of Viread[®], if applicable

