9.7. Data Analysis

• Descriptive analysis:

Categorical and ordinal variables will be described by sample size and the frequency of each modality (over the total number of responses).

Quantitative variables will be described by the number of responses, mean, standard deviation, minimum, maximum, median of all available data.

• Inferential analysis:

When deemed necessary, sub-group comparisons and/or between time point comparisons may be implemented.

Patients who are lost to follow-up or discontinue therapy for any reason, including leaving the study for non-medical reasons will be censored at the discontinuation date. Person time will be computed from baseline to discontinuation and used as such for any time to event analysis.

• Multivariate analysis

The potential dependence of treatment outcome frequency with other variables or baseline characteristics will be investigated through multivariate analysis.

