11. MANAGEMENT AND REPORTING OF ADVERSE EVENTS

11.1. Adverse Events

An **adverse event** (AE) is any untoward medical occurrence in a clinical study subject administered a pharmaceutical product, which does not necessarily have a causal relationship with the treatment. An AE can therefore be any unfavorable and/or unintended sign, symptom, or disease temporarily associated with the use of a medicinal product, whether or not considered related to the medicinal product. AEs may also include lack of efficacy, overdose, medication error, drug abuse/misuse reports or reports of AEs in infants following exposure from breastfeeding. Preexisting events that increase in severity or change in nature during this non-interventional study will also be considered AEs.

An AE does not include the following:

- Medical or surgical procedures such as surgery, endoscopy, tooth extraction, and transfusion. The condition that led to the procedure may be an AE and should be reported.
- Situations where an untoward medical occurrence has not occurred (eg, hospitalization for elective surgery, social and/or convenience admissions)
- Any medical condition or clinically significant laboratory abnormality with an onset date before the consent form is signed. These are considered to be preexisting conditions and should be documented on the medical history CRF (if applicable).

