11.2.1. Assessment of Causality for Study Drugs and Procedures

The investigator or qualified subinvestigator is responsible for assessing the relationship to drug therapy using clinical judgment and the following considerations:

- No: Evidence exists that the AE has an etiology other than the drug. For SAEs, an alternative causality must be provided (eg, preexisting condition, underlying disease, intercurrent illness, concomitant medication).
- Yes: A temporal relationship exists between the AE onset and administration of the drug that cannot be readily explained by the subject's clinical state or concomitant therapies. Or, the AE appears with some degree of certainty to be related, based on the known therapeutic and pharmacologic actions or AE profile of the drug. In case of cessation or reduction of the dose, the AE may abate or resolve and it may reappear upon rechallenge.

It should be emphasized that ineffective treatment should not be considered as causally related in the context of AE reporting.

11.3. Investigator Requirements and Instructions for Reporting Adverse Events and Serious Adverse Events to the CRO

During the defined study period (month 36 to months 72), each investigator has to document all Adverse Events he becomes aware of including seriousness and causality in the eCRF system within 24 hours. These are automatically forwarded via the eCRF system to the CRO safety department.

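### Person-time runs from GEMINIS baseline for a cohort selected at month 36, so rates of entry-barring events, and rates using only month 36–72 events, are understated about twofold or more

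*Protocol*

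**What the plan says.** All references are to the protocol.

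- **Clock (9.7).** Patients lost to follow-up or stopping therapy are censored at that date. Then: "Person time will be computed from baseline to discontinuation and used as such for any time to event analysis".
- **Meaning of baseline (9.4.1).** "VIR-life baseline data is the data that was collected at GEMINS baseline". This is month 0 of GEMINIS, when Viread was started.
- **Entry condition (9.2).** "Patients completing 3 years in GEMINIS and still receiving a Viread[®]-containing regimen may roll over into this study".
- **Event window (11.3).** "During the defined study period (month 36 to months 72), each investigator has to document all Adverse Events he becomes aware of". Section 11.1 adds to the list of what is not an adverse event: "Any medical condition or clinically significant laboratory abnormality with an onset date before the consent form is signed".
- **Size and source.** 250 patients are planned (9.5), out of 400 enrolled in GEMINIS (7.3).

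No section provides for entry into the risk set at roll-over. None says whether events recorded in GEMINIS enter the numerator of a VIR-Life time-to-event analysis.

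**The concern.** A patient who died, was lost or permanently stopped Viread in the first 36 months cannot be in VIR-Life. Every enrolled patient nevertheless brings those 36 months into the denominator. For such events that time is immortal: it is guaranteed event-free by the way the cohort was formed.

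A second route leads to the same dilution. If a rate takes its events from the VIR-Life reporting window alone but its person-time from month 0, a three-year numerator is divided by a denominator of up to six years.

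Both errors make the drug look safer. VIR-Life is a post-authorisation safety study with six-year safety and tolerability among its objectives (Section 8), so the direction matters. Nor is this a detail left open for the SAP. The protocol itself fixes the time origin and applies it to every time-to-event analysis, so a SAP that corrects it would depart from the protocol.

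**Working it through.** The protocol states no rate, event count or person-time total, so there is no figure to reproduce. The check is person-time arithmetic.

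**Inputs from the protocol:** N = 250 (9.5); entry after 3 years on treatment (9.2); event window months 36–72 (11.3); clock from month 0 (9.7 with 9.4.1). **Assumed, not in the protocol:** annual exit d, event hazard r, and share g of GEMINIS events counted.

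**Step 1. One patient who leaves at month T, numerator limited to months 36–72.** Ratio of the computed rate to the rate in the VIR-Life window = (T − 36)/T.

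- T = 48: 12/48 = 0.25
- T = 60: 24/60 = 0.40
- T = 72: 36/72 = 0.50

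**Step 2. Whole cohort, complete follow-up.** Months 36–72 give 250 × 3 = 750 person-years. From month 0 the total is 250 × 6 = 1,500. Ratio 750/1,500 = 0.50. This is the ceiling, because any exit before month 72 shrinks the observed part but not the first three years.

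**Step 3. Whole cohort with exits after month 36.** With h = −ln(1 − d), observed person-years are PY = 250 × (1 − e^(−3h))/h, and the ratio is PY/(PY + 750).

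| Assumed annual exit d | PY, months 36–72 | PY from month 0 | Ratio |
|---|---|---|---|
| 2% | 727.7 | 1,477.7 | 0.49 |
| 5% | 695.1 | 1,445.1 | 0.48 |
| 10% | 643.0 | 1,393.0 | 0.46 |
| 20% | 546.7 | 1,296.7 | 0.42 |

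**Step 4. Cumulative six-year risk of an entry-barring event.** With a constant hazard r, the true risk is 1 − e^(−6r). The enrolled cohort followed from month 0 shows no events before month 36, so its curve reaches only 1 − e^(−3r).

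| Assumed r per year | Apparent | True | Ratio |
|---|---|---|---|
| 1% | 3.0% | 5.8% | 0.51 |
| 2% | 5.8% | 11.3% | 0.51 |
| 5% | 13.9% | 25.9% | 0.54 |

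**Step 5. Events that do not bar entry.** If a share g of the month 0–36 events is counted, with a constant rate and full follow-up, the ratio is (3g + 3)/6. For g = 0, 25%, 50%, 75% and 100% this gives 0.50, 0.625, 0.75, 0.875 and 1.00. With all GEMINIS events counted there is no dilution.

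**The case against.** The strongest reply is that months 0–36 were not unobserved. Section 9.1 says patients were followed prospectively through three years of GEMINIS, and the objectives in Section 8 cover six years. HBeAg or HBsAg loss, ALT normalisation, and renal changes or adverse events that do not end treatment leave a patient eligible. Patients were at risk of these from month 0, and GEMINIS baseline is the natural origin for a six-year estimate. The one time-to-event figure in the protocol, the Kaplan–Meier estimate of HBsAg loss in Table 2, is of this kind. Section 11.3 sets a reporting window and does not define the analysis dataset.

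This stands. A reader might infer from Section 9.7 that every patient brings three event-free years for every outcome, so that all VIR-Life rates are halved. The protocol does not support that. The halving applies only where the event bars entry or where the numerator is confined to months 36–72, and the protocol never says that it is so confined.

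It is also fair that Section 9.7 treats discontinuation as censoring rather than as an event, that death is not a named outcome variable in Section 9.3, and that no particular incidence rate is planned. The stopping and death hazards above are therefore illustrations.

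The reply does not rescue the rule for entry-barring events. Counting the enrolled patients' GEMINIS events cannot help there, because selection leaves none to count. For the other outcomes it leaves the numerator window unstated.

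**Conclusion.** The point holds within limits. Section 9.7 fixes a clock that starts 36 months before the cohort is formed and provides no delayed entry. For death, lasting discontinuation and events that lead to them, and for any rate built only on month 36–72 events, the computed rate is at most 0.50 of the rate in the VIR-Life window. It is 0.49 to 0.42 under assumed exits of 2% to 20% per year. Apparent six-year risks of entry-barring events fall to roughly 0.51 to 0.54 of the true value for assumed hazards of 1% to 5% per year.

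Outcomes that leave a patient eligible, with GEMINIS events included, are not diluted. Survivor selection remains for them, but no factor can be put on it from the protocol.

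The primary objective, a description of HBV-DNA, does not use this rule. The flaw bears on safety statements if time-to-event analyses are run, so it should be fixed but does not undermine the study as a whole.

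**What to change.** Replace the person-time sentence in Section 9.7 with three rules.

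1. **Entry-barring events, and rates limited to the VIR-Life window.** Keep time since Viread start as the time scale, but enter each patient into the risk set at roll-over (left truncation at about month 36). Use the actual roll-over date. GEMINIS enrolment began in May 2009 (7.3), so the earliest patients reached month 36 in May 2012, about a year before the planned start of VIR-Life data collection (Section 6).
2. **Rates or cumulative estimates for months 0–72.** Use all 400 GEMINIS patients from Viread start, with events from both studies, and censor patients who did not roll over at their last GEMINIS contact.
3. **Other outcomes.** Keep the baseline clock, count GEMINIS events in the numerator, and state for each endpoint that numerator and person-time cover the same window. Report that the cohort is conditional on reaching month 36 on treatment.

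While the passage is open, reconcile the censoring at discontinuation in Section 9.7 with Section 9.3, which continues documentation to month 72 after Viread is stopped. This decides where person-time ends.

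The cost is a change of wording, some extra analysis and use of the existing GEMINIS data. Estimates under rule 1 say nothing about the time before roll-over, and the rates will look less favourable. Rule 2 assumes that data from GEMINIS patients who did not roll over may be used, which the protocol does not address.

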9.8. Quality Control

The electronic data entry system will contain automatic checks for data completeness and inconsistent data.

9.9. Limitations of the research methods

In a non-interventional study all decisions on the management of the patient are made solely by the treating physician. This also includes the frequency of the evaluation of lab values and other collected variables. Documentation of study variables must not be made obligatory. Missing data of unpredictable extent can occur.

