4. PROTOCOL SYNOPSIS/ABSTRACT

Gilead Sciences GmbH [name] Germany

Study Title:	VIR-Life : Prospective assessment of the real-life treatment outcomes of six years of Viread [®] in CHB following-up on the German Multicenter Non-Interventional Study GEMINIS		
Rationale and Background:	The efficacy and safety of TDF is well established by data from randomized controlled trials (RCTs) in various patient populations, such as the Gilead sponsored studies GS-US-174-102 and GS-US-174-103 in treatment naïve patients, or GS-US-174-106, GS-US-174-115 and GS-US-174-121 in patients previously treated with oral antivirals.		
	Clinical studies, such as RCT's investigate the efficacy and safety of a drug in predefined populations, therefore providing high internal validity. Data generated in real-life settings allows for investigating the external validity of the effects seen in RCTs. Thus the real-life treatment outcomes of the drug can be investigated in observational studies such as non-interventional studies (NIS).		
	The real-life treatment outcomes of Viread [®] have been investigated in GEMINIS for a period of 3 years. VIR-Life is the roll-over non- interventional study from GEMINIS to allow the prospective evaluation of the real-life treatment outcomes for additional 3 years.		
Research Question and	The primary objective of this study is as follows:		
Objectives:	• Prospectively describe the virological response, defined as HBV- DNA concentration, during 6 years Viread [®] treatment for CHB in a real life setting.		
	The secondary objectives of this study are to evaluate the:		
	• Safety and tolerability of 6 years of Viread [®] in CHB in a real life setting		
	 Adverse drug reactions (AR) (unrelated Adverse Events (AEs) will also be listed in the report) 		
	• Renal safety		
	Estimated creatinine clearance (eCrCl)		
	Serum creatinine level		

Serum phosphorus level			
	• Histological improvement of the liver		
Study Design:	Prospective non-interventional multicenter cohort post-authorization safety study (single treatment case series)		
Population / Setting:	Roll-over study in adult, HBV-mono-infected CHB patients who started CHB treatment with Viread [®] in GEMINIS		
Duration of Study:	3 years after rolling over from GEMINIS		
Variables: Documentation of routine visits at month 48, 60 and 72, covering following parameters (if available):			

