9.3. Variables

In this non-interventional post-authorization safety study the time the subject has taken Viread[®] is the exposure of interest. Outcome variables are the collected clinical and laboratory parameters, i.e.:

Primary outcome variable:

- Virology
 - Serum HBV-DNA

Secondary outcome parameters are:

- Serology
 - HBeAg/anti-HBe (qualitative)
 - HBsAg/anti-HBs (qualitative)
- Biochemistry parameter
 - o ALT
- Renal function parameters

- Serum creatinine
- Creatinine Clearance (estimated via Cockcroft-Gault, MDRD or CKD Epi formula)
- Serum phosphorus
- Liver synthesis parameters
 - o Albumin
 - o Bilirubin
 - Thrombocytes
 - Prothrombin time [i.e. Quick-Value]
- Safety parameters
 - Adverse events
 - Special Situations; pregnancies, medication error, abuse, misuse, overdose, lack of effect, adverse events in infants following exposure from breastfeeding and adverse events associated with product complaints
- Incident cases of co-infections
 - o HIV
 - o HCV
 - o HDV
- Co-morbidities (incident and prevalent cases)
 - o Ascites
 - o Jaundice
 - Diabetes mellitus
 - Lipometabolic disorders
 - o Coronary heart disease
 - Hypertension

- Alcohol consumption per week
- Liver histology and HCC
 - Liver biopsy results
 - o Fibroscan
 - o HCC
- Dosing and dose alterations
- Combination therapy
- Treatment discontinuations
 - Patients discontinuing Viread should not be discontinued from study follow up. All study variables in these patients shall be documented in VIR-life until month 72

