9.6. Data Management

The study will use an electronic data entry system (eCRF), all users will receive specific access codes to enable them to enter their data. The electronic data entry system will contain automatic checks for data completeness and inconsistent data.

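### Section 9.9 rules out any duty to enter study data, which goes further than the protocol's own non-interventional definition and conflicts with Sections 9.3 and 9.4 and the synopsis

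*Protocol*

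**What the plan says.** Section 9.9 makes two statements in sequence. The first leaves patient management to the physician and adds: "This also includes the frequency of the evaluation of lab values and other collected variables". The second is about recording: "Documentation of study variables must not be made obligatory. Missing data of unpredictable extent can occur". It contains no exception for results already in the medical record.

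Other parts of the protocol bear on the same question:

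- **Section 9.4, definition.** A non-interventional study requires "that the protocol does not stipulate or dictate on the diagnosis, therapeutic decisions and follow-up of the individual patient".
- **Section 9.4, data flow.** Data come from the visit closest to months 48, 60 and 72, each within 3 months either way. Then: "This data will then be manually transcribed by the investigator into electronic case record form (eCRF)".
- **Synopsis, Variables.** Routine visits are documented, "covering following parameters (if available)".
- **Section 9.3, patients who stop Viread.** "All study variables in these patients shall be documented in VIR-life until month 72".
- **Section 9.6, repeated in 9.8.** "The electronic data entry system will contain automatic checks for data completeness and inconsistent data".
- **Section 9.7.** Category frequencies use the number of responses as denominator, and quantitative variables are summarised on the data available.
- **Section 11.3.** Entry of adverse events within 24 hours is obligatory from month 36 to month 72.

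**The concern.** Leaving the ordering of tests to the physician is what makes the study non-interventional. Leaving the entry of an existing result to the site is a different rule, and 9.9 passes from one to the other as if they were the same.

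If a site follows 9.9 literally, a missing HBV-DNA or creatinine value has two possible causes: the test was not done, or it was done and not entered. The first is an unavoidable feature of routine care. The second is avoidable and could differ among the roughly 25 sites. Since the descriptive results are computed on what was entered, an omitted value simply leaves the denominator. No later analysis can separate the two causes if the distinction was never collected.

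**Working it through.** **1. The wording.** No figure in the protocol is in dispute, so the check is to set the passages side by side.

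| Place | Subject | What it implies for a result already on file |
|---|---|---|
| 9.9, frequency sentence | Testing | Nothing; concerns how often values are measured |
| 9.9, documentation sentence | Recording | Entry may not be required |
| 9.4, definition | Diagnosis, therapy, follow-up | Entry may be required; transcription is none of these |
| 9.4, data flow | Recording | Entry is expected |
| Synopsis | Recording | Entry depends on availability, not on site choice |
| 9.3, patients who stop Viread | Recording | Entry is required |

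The documentation sentence in 9.9 cannot be reconciled literally with the last three rows, and the definition does not call for it. Section 7.3 describes GEMINIS in a similar way: documentation is named separately from treatment decisions, and both were left to the physician alone. That makes the literal reading of 9.9 a fair one. The protocol also imposes recording duties elsewhere without treating them as interventional: adverse events (11.3) and reasons for not enrolling eligible patients (9.2.3).

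**2. The safeguards.** The checks in 9.6 and 9.8 are not described as comparing the eCRF with the medical record, and under 9.9 a flagged blank need not be filled. Monitoring in 12.3.1 is conditional on a visit taking place and verifies what has been recorded.

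**3. Size, as illustration only.** Inputs: N = 250 (9.5), m values entered, and an assumed p = 90% suppressed among them. The protocol gives no month-72 figure.

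- Lower bound (no missing patient suppressed): p × m / N
- Upper bound (all missing patients suppressed): (p × m + N − m) / N
- Width: (N − m) / N, which does not depend on p
- Wald 95% half-width: 1.96 × √(p(1 − p)/m)

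| m | Missing | Lower | Upper | Width (points) | Half-width (points) |
|---|---|---|---|---|---|
| 238 | 12 | 85.7% | 90.5% | 4.8 | 3.8 |
| 225 | 25 | 81.0% | 91.0% | 10.0 | 3.9 |
| 200 | 50 | 72.0% | 92.0% | 20.0 | 4.2 |
| 159 | 91 | 57.2% | 93.6% | 36.4 | 4.7 |

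With all 250 values the half-width is 3.7 points, so precision suffers little. The exposure is to selective omission. These widths reflect all missing values, whatever the cause. Only values that exist on file but were not entered can be attributed to 9.9, at 1/250 = 0.4 points each, and their number is unknown.

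The last row borrows the only availability figure in the protocol: GEMINIS month-24 creatinine clearance, 255/400 = 63.75% (Sections 7.3 and Table 3), and 63.75% of 250 rounds to 159.

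**The case against.** The strongest reply is that 9.9 is a limitations section. Its sentence follows one on test frequency and leads into a warning about missing data, so the authors may have meant only that values cannot be forced to exist. The operative rule would then be 9.4, which directs transcription for all patients, and 12.1.3 holds investigators to the protocol's procedures. This is a plausible account of intent, and it limits the point to one sentence that needs correcting. It does not remove the point: 9.9 speaks of documentation, is worded as a prohibition and is part of the protocol that sites must follow.

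Three further objections stand in whole or in part.

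- **On and off treatment.** A reader might infer a stricter entry standard for patients who stop Viread than for those who continue. The protocol does not support this. The 9.3 sentence belongs to an instruction to keep such patients in follow-up, and 9.4 already directs transcription for everyone. For patients on treatment the conflict is with 9.4, not 9.3.
- **HCC.** A reader might infer that incident HCC could go unrecorded. It meets the adverse event definition in 11.1, and 11.3 makes entry mandatory. Laboratory abnormalities that lead to a drug change are covered likewise (11.1.3). Lack of effect must be reported as a special situation (11.4), but such reports do not supply the HBV-DNA values to be described. The gap therefore concerns HBV-DNA and routine renal results.
- **Status fields.** Their design is usually left to data-management documents, so their absence is not in itself a protocol error. What the protocol fixes badly is the rule that would make them unenforceable.

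**Conclusion.** The concern holds as a conflict in the stated data-entry rule. Section 9.9 forbids a requirement that the non-interventional definition leaves open and that 9.3, 9.4 and the synopsis presuppose. Followed literally, it permits avoidable missing HBV-DNA and routine renal values that cannot be told apart from tests not done.

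The size is unknown. A reader might take 64% as a forecast of completeness in VIR-Life, or suppose that some fixed share of missing values could be recovered from the records. Neither is supported. The GEMINIS figure mixes drop-out, untested and unentered values, concerns creatinine clearance rather than HBV-DNA, and counts everyone enrolled, whereas VIR-Life takes patients who completed three years and still receive Viread (9.2). No source gives a recoverable share.

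Nor do the documents show that sites withheld results, that entry differed between offices and hospitals, or that omission depended on the result. These are possibilities that the rule leaves open. The argument about denominators applies to the descriptive summaries; time-to-event analyses under 9.7 use censored person-time. No sample-size figure is affected.

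**What to change.** Replace the documentation sentence in 9.9 with wording such as:

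*Performance of assessments is not obligatory. Results for study variables available in the medical record at the visit closest to each documentation time point (within 3 months either way, as in 9.4) are to be entered, for patients on and off Viread alike.*

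Tying the duty to the closest visit keeps the selection rule in 9.4. A duty to enter every result in the window would give several values per time point with no rule for choosing among them.

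For HBV-DNA and the renal variables, record *not done* or *not seen* when no result exists, and let the completeness checks already planned in 9.6 query blanks. The status field can be specified in the eCRF guidance. State also that 9.9 does not override the adverse event duty in 11.3, since 9.3 lists adverse events among the outcome variables.

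No additional test or visit is involved. The cost is slightly longer data entry and more queries to sites.
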